### **3.8 Recruitment, Retention & Follow-up**

Recruitment is limited to eligible patients admitted and consented at study sites. Based on baseline recruitment levels, the target sample size of 432 is feasible with about 9 participants per site per year. This is an in-patient intervention for the first 7 days of ICU care where intervention ICU staff are trained on intervention delivery as part of their patient care. Other data will be obtained from the health records. Follow-up data collection will be attempted at three months post-admission and can be completed in-person, via telephone, or from the health record. If unable to complete follow-up by four months, the participant will be designated lost-to-follow-up, but in-hospital data will be included. There is no incentive for participation offered to patients at any stage.

[figure not shown]
**PEGASUS Participant Timeline**

## CHAPTER 4. INTERVENTION

The PEGASUS program intervention has multi-level components to increase TBI guideline adherence. It will be implemented from October 2020-September 2023. The patient level clinical care pathway is implemented for each eligible, consented patient at an intervention site for up to seven days of their ICU stay. Intervention site care providers supply perspectives and knowledge elements quarterly. At the hospital level, intervention sites participate in quarterly focus groups, morbidity and mortality case reviews and quality improvement efforts, and regular motivational interviewing informed (MI) check-ins with site PIs facilitated by CIIC.

### 4.1 Intervention Model

## 4.2 Implementation Readiness

The four overarching program attributes are intent to benefit children with severe TBI (the who), inclusion of evidence-based acute care severe TBI recommendations (the what), program flexibility (the how), and capacity building (the goal). Multilevel refers to outer setting, inner setting, individual, and implementation process. The PEGASUS program meets criteria for innovation domain of the Consolidated Framework for Implementation Research constructs. Actions are given in chronological order. Process times may vary but ranged from 2-3 months. Timeline for process completion may vary depending on local needs.

## 4.3 TBI Guideline Adaptations

During the baseline study period, the full study team, including the sites provided input on TBI guidelines in the local context and impact on the relevant indicators in the guideline adherence calculation scorecard.

## 4.4 PEGASUS Pathway

[figure not shown]
The PEGASUS pathway does not prescribe specific drug doses or treatments but provides guidelines that inform the clinical assessment and treatment for individual patients. The PEGASUS program has been iteratively refined for use in the South American context and includes additional nursing resources for rounding and family education guides to encourage engagement.

As a pragmatic implementation science study with quality improvement efforts, the components of the study are designed to be adaptable to support sites' needs and to evaluate process measures to address reach (number of patients), dose (% processes implemented), and fidelity (variance from recommended

processes and timely clinical pathway adoption). The Theoretical Domain Framework (TDF) and the Determinants of Implementation Behavior Questionnaire (DIBQ) guide these efforts.

#### **4.5 Case Review and Quality Improvement (QI) Intervention Cycle**

This QI Cycle is used to support intervention implementation. Intervention sites will select a PEGASUS case to review quarterly with their ICU team. The case review form and follow-up corrective actions will be assessed by the CIIC/UW team.

#### **4.6 Focus Groups and MI Check-Ins**

The purpose of the quarterly focus groups and primarily bi-monthly (adaptive) MI check-ins as part of the intervention is to:

- Facilitate engagement in the study
- Promote adherence with PEGASUS protocols
- Address unmet needs while promoting site PI and clinician autonomy

It utilizes adaptable discussion guides based on the TDF and DIBQ domains to maintain engagement to promote changes in the behavior of the site PI and coordinators that translates into improved implementation of the PEGASUS Pathway and the goal of increasing BTF guideline adherence.

### **CHAPTER 5. SAFETY REPORTING & ADVERSE EVENTS**

#### **5.1 Complications Reporting**

The UW IRB has determined that the study and the intervention pose minimal risk to participants. However, due to the nature of severe TBI injuries and ICU hospitalization it is anticipated that adverse events and complications, including death, will occur. Site PIs will report to a complications form in the database. The complications form tracks the occurrences, type, and severity (grave, moderate, or mild) of complications that occur. Shock, pneumonia, peritonitis, intraparenchymal hemorrhage, and

arrhythmia are specifically identified, and other complications are noted as free text. We have pre-intervention baseline data to assess adverse events related to patient safety or concerning trends in recruitment or follow-up data and we do not expect higher than baseline adverse events during the implementation of the intervention. If concerned about the impact of the study on an adverse event, site PIs will notify CIIC directly and the concern will be reviewed and escalated.

## **5.2 DSMB Committee**

This study has an internal Data Safety and Monitoring Board (DSMB) comprised of a small group of experts who are not part of the study team. Study PIs, CIIC co-investigators, and the research coordinator will meet with them twice per year to review study status, recruitment, and adverse events, or in the event of an escalation.

The DSMB will review participant recruitment, mortality, surgery type and frequency, and adverse events from the complications form. The study team will categorize complications according to body system. The DSMB will remain blinded to study arms unless a specific, unanticipated concern needs to be addressed. Reports from the meetings will also be submitted to the UW IRB to comply with IRB requirements.

## **CHAPTER 6. TRAINING PLAN**

The overarching methodology of training for this study is a train-the-trainer model. The University of Washington (MSV) and Children's National Hospital (MJB) trained CIIC (NG, SBL, GP) partners and CIIC investigators trained site PIs in study procedures. Materials were co-developed by the study team. Questions from sites were first fielded in real time and per schedule by CIIC and escalated to MSV and MJB, as deemed necessary by CIIC.

### **6.1 Data Collection Training**

[figure not shown]
Prior to participant enrollment for baseline data collection, all sites are trained in screening and consenting study participants. Training is conducted in medical record abstraction for patient level usual care data. After introducing the database and data collection forms, sites abstract a medical record from a sample patient as practice. Additional organizational level forms are also reviewed and the first round of these repeated forms are completed. Annually, data collection will be covered during booster trainings and other individual data entry issues will be addressed within the communications with the sites.

UW trains CIIC on concept of process flow and value stream mapping through app demonstration and real-world examples. CIIC trains all site PIs on concepts of process flow and value stream mapping (VSM). Process flows are workshopped by site PIs who provided annual surveys of the ICU workflow.

### **6.2 Training Cycle for Intervention Implementation**

Below is the PEGASUS Training Cycle for Intervention Implementation describing the timing and steps of implementation training for the intervention sites prior to intervention implementation. Annually,

common intervention concerns will be covered during booster trainings and other individual issues will be addressed within the communications with the intervention sites.

### 6.3 PEGASUS Pathway Training

[figure not shown]
CIIC will lead training with intervention sites prior to implementation to review BTF guidelines and show how they integrate with the PEGASUS Pathway using an example case. Additional nursing resources and rounding tool and a family guide, co-developed by UW and CIIC, will be introduced and provided to support training of ICU nursing staff and for families, respectively.

Intervention sites (site PIs and site coordinators) will then lead training for their ICU staff who care for eligible participants.

### 6.4 Case Review and Quality Improvement Training Details

The case review training module is adapted from World Health Organization (WHO) trauma quality improvement guidelines by UW with CIIC input. CIIC (SL) attended a Pan-American Health Organization (PAHO)-led training on the topic in 2019. The goal of the case review and QI training is to build capacity at sites for local QI processes. Part One is a case review module consisting of a self-directed training module (recorded presentation) and Part Two, a group case review training activity led by CIIC of three

local cases (deidentified) at the implementation training to be conducted prior to implementation at intervention sites. Annually, QI topics were revisited in booster trainings.

## 6.5 Focus Group and Motivational Interviewing (MI) Informed Check-In Facilitation Training

Using the train-the-trainer model, UW provides initial facilitation trainings (two sessions) to CIIC on the use of motivational interviewing methods for the regular check-in communication at intervention sites and for focus groups with site PIs, coordinators, and ICU staff. The study team provides support on facilitation to CIIC as needed.

The primary components of this training include:

- Principles of MI
- Basic Principles of a Person-Centered Approach to Behavior Change
- The Flow of MI
- Reveal Discrepancies and Respond to Resistance

- Strengthen Commitment and Make a Change Plan
- Review and Role Play of the Focus Group and Check-In Discussion Guides

## **CHAPTER 7. COMMUNICATIONS PLAN**

UW communicates internally and with CIIC at least weekly. Study PIs and CIIC meet biweekly, and the PEGASUS Argentina study team meets monthly. Meeting minutes will be maintained. Other sub-meetings and ad hoc communications for specific tasks facilitate activities in-between regular meetings. All-team meetings with PIs, study team, CIIC, and site PIs and coordinators (separated by study arm) are annual, via Zoom or in-person, as feasible.

CIIC conducts day-to-day management of intervention delivery and implementation of activities, data entry support, training of study site staff, and direct weekly communication with study sites. Site communication and monitoring is conducted by CIIC to educate, support, and solve problems with data collection, intervention implementation, and quality improvement, with additional input from study PIs and co-investigators as necessary. In-person site visits are conducted as feasible due to travelling restrictions.

## **CHAPTER 8. DATA COLLECTION, MANAGEMENT, & ANALYSIS**

### **8.1 Data Management**

[figure not shown]
The purpose-built, password-protected database is maintained on a dedicated server and has logic coding and input parameters to ensure legal variable values. Qualitative data for the provider- and hospital-level intervention support include free text response in questionnaires and case reviews, notes, and summaries of focus groups and MI check-ins. Data completion is assessed monthly by UW and CIIC study staff.

### **8.2 Data Confidentiality**

Participant identification codes are assigned at the sites at the time of screening. Hospital site PIs and study coordinators have access to personal identifiers of their site's enrolled patients and medical records through their dual roles as researchers and care providers. CIIC and U.S.-based study staff have access to the full dataset through the PEGASUS database, but without protected personal information like names, birth dates, or contact information.

[figure not shown]
### **8.3 Data Flow Model**

The Data Flow Model below shows the procedures and responsibilities for data collection, data checks, and analysis.

#### 8.4 Data Collection Timeline

Baseline data collection will occur at all participating sites from September 2019-September 2020. From October 2020-September 2023, intervention sites will collect additional data associated with the intervention implementation. The Data Collection Timeline below shows the data types collected (leftmost column) and the intervals of repeated measures.

## 8.5 Missing Data

Missing data identified during data checks will be followed-up and resolved with site PIs. Participants with missing data will be included in relevant analyses unless they specifically withdraw from the study.

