### 3.3 Site Randomization Plan

Sixteen study sites were recruited by CIIC based on willingness to participate and annual severe TBI admissions. Sites were added after the original proposal to increase the potential patient recruitment population. All sites receive compensation for data submission. Prior to randomization on July 13, 2020, three sites who had no or one enrolled patient during ten months of baseline usual care data collection were removed from the pool. The remaining sixteen sites participating were ranked by median monthly baseline enrollment, number of zero recruiting months, and total number of recruited patients and divided into four groups (Group A=highest enrollment group, Group D=lowest enrollment group). The study statistician performed computer block randomization within each group to assign to control and intervention arms at a 1:1 ratio. Participant assignment was dependent on the intervention or control arm assignment of the study hospital to which they were admitted.

Due to the nature of the intervention study team, site staff, and patients' families are aware of the site's arm assignment.

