### **3.7 Sample Size and Power**

A sample size of 432 participants is targeted for the planned parallel cluster study, which would have 80% power to detect a 18.7% higher ICU TBI guideline adherence rate with program implementation at the site level, with a two-sided alpha of 5%, and an intraclass coefficient of 0.05. Calculations included 58.6% guideline adherence rate estimate based on prior pilot work in Argentina and assumed no change in adherence rate at control sites. The study will not be sufficiently powered for secondary outcomes of patient mortality, discharge outcomes, or three-month follow-up outcomes.

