**Methods:**

1. Descriptive statistics for all measures at the facility level, within treatment and control arms. Potential differences in patient (age, sex, race/ethnicity) and injury characteristics will be examined using bivariate analyses by center using  $\chi^2$  tests (categorical) and t-tests (continuous).
2. ITT analysis: multi-level mixed effects Poisson regression with robust variance estimation and clustering by site to estimate the relative risk of PEGASUS implementation on TBI guideline adherence and stratified by extracranial injury, as described in Zou, et al.  
Per protocol: As with ITT, but potentially including implementation dose/fidelity as covariate and interaction with intervention.
3. Secondary analyses (Following ITT for primary analysis): Poisson regression with robust variance estimation and clustering by site to estimate separately the relative likelihood of program implementation on these outcomes: 1) in-hospital mortality; and 2) GOSE-Peds at 3 months post TBI, analyzing GOS score as a dichotomous measure (minor-moderate impairment vs major impairment-vegetative state and death).  
Multivariable Cox regression model to examine the marginal effect of PEGASUS on mortality during the 3 months post discharge, averaged over all centers.
4. Sensitivity analyses: repeated analysis on ICP monitoring patients
5. Subgroups: COVID effect and geographic effect

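### No method is given for survivors without a 3-month GOSE-Peds, so the default complete-case analysis over-represents deaths and can bias the risk, and the ratio if loss differs by arm

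*Protocol*

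**What the plan says.** SAP Methods item 3 lists as a secondary outcome "GOSE-Peds at 3 months post TBI, analyzing GOS score as a dichotomous measure". Death falls on the unfavourable side of the split. The model is Poisson regression with robust variance, clustered by site.

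Protocol 3.8 allows the three-month assessment to be made in person, by telephone or from the health record. If it is not complete by four months, "the participant will be designated lost-to-follow-up, but in-hospital data will be included".

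Protocol 8.5 has sites resolve missing items where possible and then states: "Participants with missing data will be included in relevant analyses unless they specifically withdraw from the study". Protocol 3.5 removes the data of anyone who withdraws.

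Neither document mentions imputation, weighting, a sensitivity analysis for missing outcomes, or an expected loss rate. The only sensitivity analysis in the SAP repeats the analysis in ICP-monitored patients.

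**The concern.** A regression model cannot use a child who has no outcome value. Unless a rule supplies one, that child leaves the GOSE-Peds analysis, whatever Protocol 8.5 intends by inclusion.

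The gap is one-sided. An enrolled child who dies in hospital, and whose family has not withdrawn, has a known 3-month category. A child discharged alive has one only if follow-up is completed. Missing values therefore arise among those discharged alive, and deaths take a larger share of the analysed set than of the cohort.

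Two results are at stake: the unfavourable risk in each arm, and the between-arm ratio if follow-up is better in one arm. Unequal follow-up is possible. Arm assignment is known to staff and families (Protocol 3.3), sites do the follow-up (2.3), and only intervention sites have the focus groups and check-ins meant in part to sustain engagement (4.6). The 3-month GOSE is named in the Aim 1a hypothesis, so its ratio will be read as evidence on PEGASUS.

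**Working it through.** **The plan's own figure.** The documents give no figure for this outcome. The only sample-size figure, in Protocol 3.7, is for adherence: "A sample size of 432 participants is targeted for the planned parallel cluster study". It reproduces if 18.7 is read as percentage points (58.6% to 77.3%). With 432/16 = 27 children per site and ICC 0.05, the design effect is 1 + 26 × 0.05 = 2.30. Per arm before clustering, n = (1.960 + 0.842)² × (0.586 × 0.414 + 0.773 × 0.227) / 0.187² = 93.84. Then 93.84 × 2.30 × 2 = 431.7, i.e. 432. This is context only and does not bear on the point.

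**Inputs for the check (all assumed).** D = in-hospital death; S = 1 − D; u = unfavourable proportion among followed survivors; l = proportion of survivors lost.

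**Formulas, lost survivors like followed survivors.**
- Full-cohort risk = D + S·u
- Complete-case risk = [D + S(1 − l)u] / [D + S(1 − l)]

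With D = 20%, u = 20%, l = 20%: the full-cohort risk is 0.20 + 0.80 × 0.20 = 36.0%; the complete-case risk is (0.20 + 0.64 × 0.20) / 0.84 = 39.0%.

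Results for D = 20%. The ratios are intervention/control with no true effect and 10% loss in the intervention arm.

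| u | Full cohort | l = 10% | l = 20% | l = 30% | Ratio, 10% vs 20% | Ratio, 10% vs 30% |
|---|---|---|---|---|---|---|
| 20% | 36.0% | 37.4% | 39.0% | 41.1% | 0.958 | 0.911 |
| 30% | 44.0% | 45.2% | 46.7% | 48.4% | 0.969 | 0.934 |

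Over a wider grid (D 10-30%, u 20-40%, l 10-30%) the risk is overstated by 0.6 to 6.4 percentage points. Null ratios are 0.956 to 0.985 for 10% vs 20% loss and 0.909 to 0.966 for 10% vs 30%. If the intervention arm loses more (30% vs 10%), they are 1.035 to 1.100. Equal loss gives exactly 1.000.

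**Direction when lost survivors differ.** Let u_L be the unfavourable proportion among lost survivors. Then complete-case risk − full-cohort risk = S·l·(complete-case risk − u_L). The sign changes where u_L equals the complete-case risk. For D = 20%, u = 30%, l = 20%, S·l = 0.16:
- u_L = 30%: 0.16 × (0.467 − 0.30) = +2.7 points
- u_L = 60%: 0.16 × (0.467 − 0.60) = −2.1 points
- u_L = 0% or 100%: +7.5 or −8.5 points, so the full-cohort risk could lie anywhere from 39.2% to 55.2%

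**Equal loss with a true effect.** With D = 15% vs 25%, u = 30% in both arms and 20% loss in both, the true ratio is 0.405/0.475 = 0.853. The complete-case ratio is (0.354/0.83) / (0.430/0.85) = 0.843. With D = 15% vs 20% and u = 25% vs 30%, 0.824 becomes 0.826. Equal loss therefore moves a non-null ratio only slightly.

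**The case against.** The strongest reply is that the documents contain a gap, not an error. A reader might infer that the plan drops lost survivors. No sentence says so, and Protocol 8.5 speaks of including participants with missing data. That stands: the exclusion is a default consequence. But 8.5 supplies no value, so the sentence does not prevent it.

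A reader might also infer that every in-hospital death is kept. That is too strong. Protocol 3.4 lists death before consent as a reason for non-enrolment, and 3.5 removes withdrawn children's data. The imbalance concerns enrolled, non-withdrawn children only.

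A reader might take the overstatement as certain. It is conditional: if the unfavourable rate among lost survivors exceeds the complete-case risk, the bias reverses. In the two 20%-loss examples that needs more than 39.0% against 20% among followed survivors, or more than 46.7% against 30%. This is possible, and nothing in the documents rules it out.

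Unequal loss is not established either. The extra contact in the intervention arm is with site staff, not with families after discharge. Compensation for data (3.3), weekly contact with sites (Chapter 7) and monthly completeness checks (8.1) are not restricted to one arm. Follow-up from the health record may also keep loss low. These points make unequal loss a risk to plan for, not a finding.

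Finally, Protocol 3.7 declares the 3-month outcomes underpowered. That limits the weight of the result but does not remove bias from it.

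**Conclusion.** The point holds as a gap with a predictable consequence. With no rule for survivors lacking a 3-month value, the stated model runs on complete cases and deaths are over-represented.

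With D = 20%, u = 20-30%, and lost survivors resembling followed ones, the null intervention/control ratio is about 0.91 to 0.97 if loss is 10% in the intervention arm and 20-30% in the control arm. The error then favours PEGASUS. It goes the other way if the intervention arm loses more. The size rests wholly on assumed rates, since the documents give none for loss, mortality or outcome.

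The primary adherence outcome and in-hospital mortality are unaffected. The 3-month mortality analysis uses Cox regression, which can accommodate censoring; GOSE-Peds has no equivalent. For a secondary, underpowered outcome this is a change that should be made, not one that threatens the trial's main conclusion.

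**What to change.** Amend SAP Methods item 3, before outcomes are analysed by arm, to state:

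- The GOSE-Peds analysis includes all enrolled, non-withdrawn children, with in-hospital deaths coded as death.
- For children discharged alive without a 3-month value, the outcome is multiply imputed from discharge GOS, age, baseline GCS, extracranial injury, arm and site. Inverse-probability weighting among survivors on the same variables is an acceptable alternative; the choice should be named in advance.
- Complete-case results and a tipping-point analysis, including the best-case and worst-case bounds, are reported as sensitivity analyses.
- Loss to follow-up among survivors is reported by arm.

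The SAP already lists discharge GOS, extracranial injury, arm and demographics; site is the clustering unit, and GCS is assessed at eligibility (Protocol 3.4). Enrolment, consent and data collection do not change. The cost is SAP wording and modest programming, with some care over site effects given about 27 children per site. The main result would then rest on a missing-at-random assumption, which the sensitivity analyses probe.
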